1.2.2 Study Period B

Following the completion of Study Period A, participants will be offered the opportunity to continue to receive study drug until the results of the study are known. This is termed Study Period B. All *PSEN1* mutation carriers will be provided crenezumab in Study Period B regardless of treatment allocation during Study Period A, and all non-carriers will continue on placebo. Treatment allocation for both Study Periods A and B will remain blinded. Study Period B may last up to approximately 12 months depending on when participants enter Study Period B. See [Figure 2](#).

[figure not shown]
*After the primary efficacy results from Study Period A are available, the Sponsor may extend Study Period B, or initiate an OLE study for *PSEN1* E280A autosomal-dominant mutation carriers, or development of crenezumab may be discontinued.*

Figure 1 Study Design

RCT = randomized, controlled trial.

Figure 2 Study Schematic

ETA/ETB = end of treatment visit A or end of treatment visit B; OLE = open-label extension; SFU = safety follow-up; W = week.

1.2.3 Treatment Assignment and Blinding

Both *PSEN1* E280A mutation carriers and non-carriers were enrolled. The majority of participants in the *PSEN1* E280A kindred cohort from Colombia do not wish to know their *PSEN1* genotype. In most cases, the participant will not know whether he or she is a mutation carrier or a non-carrier. Participants who had their mutation carrier status

disclosed by a physician in conjunction with genetic counseling outside of the auspices of this study and are mutation carriers were eligible for the study. Genetic disclosure performed independent of this study was not required for a mutation carrier to be eligible to participate. Non-carriers who received information about their genetic status prior to the study were not included.

Participants, blinded study personnel, and the Sponsor will not know if a participant has been assigned to the active treatment or one of the two placebo treatment groups in Study Period A. In Study Period B, participants and blinded study personnel will continue to be blinded to original and current treatment assignment. Following *the data snapshot for the Study Period A primary analysis*, selected members of the Sponsor team may become unblinded for the purpose of analysis and interpretation of Study Period A data.

In Study Period A, a dynamic randomization design was used with treatment allocation assigned by the interactive voice or Web-based response system (IxRS) vendor. Mutation carriers were randomized to crenezumab and placebo arms in a 1:1 ratio. A smaller group of mutation non-carriers were assigned to placebo to conduct the study, such that autosomal-dominant AD (ADAD) family members were not required to receive information about their genetic risk and to help distinguish those changes related to the predisposition to AD from those associated with normal aging in the two placebo groups (in Study Period B, all carrier participants will be assigned crenezumab by the IxRS vendor and non-carrier participants will be assigned placebo).

While pharmacokinetic (PK) samples should be collected from participants assigned to the placebo arms to maintain the blinding of treatment assignment, PK assay results for these participants are generally not needed for the safe conduct or proper interpretation of this trial. A defined set of personnel responsible for performing PK assays and not otherwise involved in the conduct of the trial will be unblinded to participants' treatment assignments to identify appropriate PK samples to be analyzed. Samples from participants assigned to the placebo arms will not be analyzed except by request (i.e., to evaluate a possible error in dosing). In addition, PK and plasma pharmacodynamic (PD) assay results will not be released to blinded personnel until the study is unblinded.

If unblinding is necessary for participant management (e.g., in the case of a serious adverse event for which participant management might be affected by knowledge of treatment assignment), the investigator will be able to break the treatment code by contacting the IxRS. Treatment codes should not be broken except in emergency situations.

For regulatory reporting purposes, and if required by local health authorities, the Sponsor will break the treatment code for all serious, unexpected, and suspected

adverse reactions that are considered by the investigator or Sponsor to be related to study drug.

1.2.4 Independent Progression Adjudication Committee

Ascertainment of AD dementia or MCI progression will be made by the investigator. An independent progression adjudication committee (iPAC) was formed to review the information provided by the site investigators regarding participants enrolled in the trial. The iPAC will review data on:

- Participants who, in the opinion of the site investigator, appear to have progressed from not meeting criteria for MCI due to AD or dementia due to AD to meeting criteria for MCI due to AD or to dementia due to AD;
- Participants who, in the opinion of the investigator, appear to have progressed from meeting criteria for MCI due to other cause to meeting criteria for MCI due to AD or to dementia due to AD;
- Participants who, in the opinion of the investigator, appear to have progressed from meeting criteria for dementia due to other cause to meeting criteria for MCI due to AD or to dementia due to AD, and;
- A matching number of participants who, in the opinion of the investigator, do not appear to have progressed. *For each "case" the site submits, the data-coordinating center randomly selects a participant from the list of participants who have not yet been adjudicated as a progression using a random number generator. Once the participant has been identified, the data-coordinating center instructs the site to provide information needed for adjudication for that participant.*

The primary roles of iPAC members will be to:

- Provide guidance to the site and Sponsor regarding evaluation and as needed, collection of information necessary to adjudicate progression to MCI or dementia
- Review all participants' clinical information supplied in the supporting documents and make a determination as to whether the participant has progressed or not progressed from "normal cognition" (i.e., in this protocol, not meeting criteria for MCI or dementia) to MCI due to AD or dementia due to AD at the time of the most recent major clinical assessment at the site

If there is lack of consensus between the iPAC members as to progression of an individual participant, they will confer and arrive at a consensus. If the members' opinion differs with that of site investigators, one or both members will correspond with site investigators and attempt to arrive at a consensus. Failing that, the opinion of the iPAC will be used for purposes of statistical analysis; *the opinion* of the site investigators will be used for clinical management of the study participant. If after adjudication, both the iPAC members and site agree that the participant has not progressed, the participant will be re-adjudicated if deemed to progress by the site at a future visit.

1.2.5 Data Monitoring

An independent Data Monitoring Committee (iDMC) is being used during the conduct of this trial to periodically review unblinded safety and efficacy data. In addition to periodic review of safety and efficacy data, the iDMC may make recommendations regarding study conduct. Details of the iDMC membership and roles are detailed in the iDMC Charter.

2. STATISTICAL HYPOTHESES

The primary endpoint family consists of 2 endpoints: 1) annualized change on the Alzheimer's Prevention Initiative (API) ADAD Composite Cognitive Test total score and 2) annualized change on Free and Cued Selective Reminding Task (FCSRT) Cueing Index. The type I error is split between testing the treatment effect on the API ADAD Composite Cognitive Test total score ($\alpha=0.04$) and on the FCSRT Cueing Index ($\alpha=0.01$). If at least one of the 2 primary analyses is statistically significant, then the trial is considered positive. The primary endpoint family in the crenezumab arm and placebo arm will be compared among mutation carriers and tested using a random coefficient regression model (RCRM) with the null and alternative hypotheses as follows.

- API ADAD Composite Cognitive Test total score:
 - H_0 : There is no difference in annualized change on the API ADAD Composite Cognitive Test total score between the crenezumab and placebo arms among mutation carriers
 - H_1 : There is a difference in annualized change on the API ADAD Composite Cognitive Test total score between the crenezumab and placebo arms among mutation carriers
- FCSRT Cueing Index:
 - H_0 : There is no difference in annualized change on FCSRT Cueing Index between the crenezumab and placebo arms among mutation carriers.
 - H_1 : There is a difference in annualized change on FCSRT Cueing Index between the crenezumab and placebo arms among mutation carriers.

Details on the type I error control are described in Section [3.1](#).

3. SAMPLE SIZE DETERMINATION

This study will enroll up to 300 participants: up to 200 participants will be enrolled in the carrier cohort and up to 100 participants will be enrolled in the non-carrier cohort. Participants in the carrier cohort will be randomized in a 1:1 randomization ratio to active treatment or placebo. The study was initially powered to compare the mean change from baseline over 260 weeks in the API ADAD Composite Cognitive Test total score between the active treatment group and the placebo group. Assuming a 25% dropout rate with use of two-sided testing at the overall 0.05 level, a placebo group coefficient of variation of 65% for the Week 260 change scores ($= 100\% \times$ standard deviation of

[figure not shown]
placebo participant change scores/mean of placebo participant change scores) and 100 participants per arm, the study will have at least 80% power to detect a true effect of 30% reduction of the mean decline in the API ADAD Composite Cognitive Test total score in the placebo group using a t-test. Participants in the non-carrier cohort will all receive placebo and will be included in the study in order to maintain the genotype blind.

3.1 TYPE I ERROR CONTROL

A graph-based ([Bretz et al. 2009](#); [Bretz et al. 2011](#); [U.S. Food and Drug Administration \[FDA 2017\]](#)) testing procedure will be used to ensure the family-wise type I error will be controlled at a two-sided $\alpha=0.05$. In [Figure 3](#), we illustrate how hypothesis testing of the primary endpoint family will be performed. The key secondary endpoints will be tested hierarchically at $\alpha=0.05$ ordered by the following, only if both primary endpoints are significant; after the first occurrence of the p -value >0.05 in the list below, subsequent hypothesis testing will stop.

1. Annualized rate of change in mean fibrillar amyloid accumulation in a composite region (including frontal, temporal, parietal, and cingulate cortices) with a subcortical white matter reference region using florbetapir PET
2. Time to progression from preclinical AD to MCI due to AD or from preclinical AD to dementia due to AD
3. Annualized rate of change in the Clinical Dementia Rating (CDR) Scale-Sum of Boxes
4. Time to progression to non-zero in CDR global score
5. Annualized rate of change in a measure of overall neurocognitive functioning: Repeatable Battery for the Assessment of Neuropsychological Status (RBANS) total score

Figure 3 Graph-Based Testing Procedure for Type I Error Control

API=Alzheimer's Prevention Initiative; ADAD=autosomal-dominant Alzheimer's disease; FCSRT=Free and Cued Selective Reminding Task.

The arrows in Figure 3 denote the direction of α propagation; the notation ε indicates a positive real number close to zero, which in our case indicates the potential to pass α from the FCSRT Cueing Index to key secondary endpoints but only if it is not necessary to pass α from the FCSRT Cueing Index to the API ADAD Composite Cognitive Test total score. In the following, we illustrate how the procedure works in a few examples.

- **Example 1:** p-value from testing API ADAD Composite Cognitive Test total score hypothesis=0.045; p-value from testing FCSRT Cueing Index hypothesis=0.005. Our graph-based approach will declare statistical significance on both primary endpoints and $\alpha=0.05$ is passed to key secondary endpoints being tested in our specified order.
- **Example 2:** p-value from testing API ADAD Composite Cognitive Test total score hypothesis=0.06; p-value from testing FCSRT Cueing Index hypothesis=0.005. Our graph-based approach will declare statistical significance only on the FCSRT Cueing Index and no α is passed to key secondary endpoints.
- **Example 3:** p-value from testing API ADAD Composite Cognitive Test total score hypothesis=0.03; p-value from testing FCSRT Cueing Index hypothesis=0.03. Our graph-based approach will declare statistical significance on both primary endpoints and $\alpha=0.05$ is passed to key secondary endpoints being tested in our specified order.
- **Example 4:** p-value from testing API ADAD Composite Cognitive Test total score hypothesis=0.03; p-value from testing FCSRT Cueing Index hypothesis=0.06. Our graph-based approach will declare statistical significance only on the API ADAD

Composite Cognitive Test total score and no α is passed to key secondary endpoints.

Before study unblinding, the Sponsor performed the blinded power (BP) analysis on the original primary endpoint (API ADAD Composite Cognitive Test total score) and the secondary clinical endpoints using data from all participants regardless of carrier status. The BP analyses assumed the same crenezumab treatment effect across all endpoints considered. The Sponsor concluded that the FCSRT Cueing Index was expected to have a CV which meets the statistical power target specified in the protocol without speculation on the treatment effect based on the blinded data. Therefore, the Sponsor decided to add the FCSRT Cueing Index to the primary endpoint family due to its expected sensitivity to change over time given its clinical relevance as a sensitive measure of episodic memory decline, a hallmark of emerging symptomatic AD, and the most commonly observed, early, and consistent neuropsychological marker of AD (Tounsi et al. 1999; Bateman et al. 2012; Caselli et al. 2020). Appendix 2 describes details of the BP analysis along with *mathematical proof* of type I error control.

4. ANALYSIS SETS

The following analysis populations are defined for Study Period A:

Population	Definition
ITT	All randomized participants, whether or not the participant received the assigned treatment; participants are grouped according to the treatment assignment at randomization \times mutation status.
mITT	All randomized participants who received at least 1 dose of study drug; participants are grouped according to the treatment assignment at randomization; all primary and secondary efficacy analyses are based on the mITT population among the mutation carriers.
Safety-evaluable	All randomized participants who received at least 1 dose of study drug; participants are grouped according to the actual treatment received \times mutation status; mutation carriers randomized to placebo and mutation non-carriers randomized to placebo who received more than 2 doses of crenezumab will be grouped in the crenezumab arm; all participants who have received no more than 2 doses of crenezumab will be further grouped together in a placebo arm, regardless of the mutation status.
Pharmacokinetic-evaluable	All safety-evaluable participants with at least 1 plasma sample, provided sufficient dosing information (dose and dosing time) is available. Participants will be grouped according to the actual treatment received; participants randomized to placebo who received more than 2 doses of crenezumab will be grouped in the crenezumab arm.

Population	Definition
Tau-ITT	Tau substudy ITT population. All participants randomized in Study GN28352 and consented to the tau PET substudy, whether or not the participant received the assigned treatment; participants are grouped according to the treatment assignment at randomization \times mutation status.
Tau-mITT	Tau substudy modified ITT population. All participants randomized in Study GN28352 and consented to the tau PET substudy who received at least 1 dose of study drug; participants are grouped according to the treatment assignment at randomization; analyses on change in tau burden are based on Tau-mITT population among the mutation carriers.
Tau-safety-evaluable	All participants randomized in Study GN28352 and consented to the tau PET substudy who received at least 1 dose of study drug; participants are grouped according to the actual treatment received \times mutation status; mutation carriers randomized to placebo and mutation non-carriers randomized to placebo who received more than 2 doses of crenezumab will be grouped in the crenezumab arm; all participants who have received no more than 2 doses of crenezumab will be further grouped together in a placebo arm, regardless of the mutation status.

ITT = intent-to-treat; mITT = modified intent-to-treat; PET = positron emission tomography.

5. **STATISTICAL ANALYSES**

5.1 **GENERAL CONSIDERATIONS**

Analyses for Study Period A includes the following:

- A primary analysis (*initial readout*) will occur after all participants have completed the Week 260 assessments
- *During Study Period B, safety analyses from Study Period A will be refreshed (due to the additional 16-week safety follow-up data accrued in Period A after the primary analysis) and reported in the final Clinical Study Report (CSR); no other analyses (e.g., primary and secondary endpoints and PK/PD endpoints) will be refreshed*

The analyses for Study Period B or the OLE study are described in Section 5.10.

All efficacy analyses will be performed on the modified intent-to-treat (mITT) population, unless otherwise specified. Participants will be analyzed according to the treatment assigned at randomization by IxRS.

All safety analyses will be performed in the safety-evaluable population, unless otherwise specified.

All data, including data collected after Week 260, will be used for the primary analysis.

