1. INTRODUCTION

This Statistical Analysis Plan (SAP) provides details of the planned analyses and statistical method for the clinical efficacy and clinical safety for Period A of Study GN28352. *The analyses specified in this document supersede the analysis plan described in the study protocol and the previous version of the SAP. After the primary analysis results from Period A of Study GN28352 are available, the Sponsor may extend Study Period B, or initiate an open-label extension (OLE) study for PSEN1 E280A autosomal-dominant mutation carriers. Key efficacy analyses and general descriptions of safety and other analyses in Period B of Study GN28352 and in the potential OLE study are also included in Section 5.10 of this SAP.*

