5.6 SAFETY ANALYSES

All safety analyses of Study Period A will be performed in the safety-evaluable population (see Section 4 for definition).

As the study participants are considered treatment-exposed during the 16-week (approximately 5 half-lives) follow-up period, adverse events reported within 16 weeks after the last dose of study drug administered in Study Period A will be included in the safety analyses from Study Period A (contrary to the description in the protocol stating they will be summarized separately). At the end of Study Period B, safety analyses on

Study Period A will be refreshed (*due to the additional 16-week safety follow-up data accrued in Period A after the primary analysis*) and reported in the final CSR.

Adverse events reported within 16 weeks after the last dose of study drug administered in Study Period B will be included in the safety analyses on Study Period B.

Safety analyses of Study Period B and/or of the potential OLE data are summarized in Section 5.10.2.

Safety will be assessed through summaries of exposure to study treatment, adverse events, changes in laboratory test results, MRI findings, changes in vital signs and ECGs, and changes in suicidality assessment.

Study treatment exposure (such as treatment duration, total dose received, and dose modifications) will be summarized with descriptive statistics.

All verbatim adverse event terms will be mapped to MedDRA thesaurus terms, and adverse event severity will be graded according to National Cancer Institute Common Terminology Criteria for Adverse Events (NCI CTCAE), v4.0. All adverse events, serious adverse events, adverse events leading to death, adverse events of special interest, and adverse events leading to study treatment discontinuation that occur on or after the first dose of study treatment (i.e., treatment-emergent adverse events) will be summarized. All adverse events will be summarized by severity and by relationship to study drug. For events of varying severity, the highest grade will be used in the summaries.

Relevant laboratory, vital signs (pulse rate, respiratory rate, blood pressure, pulse oximetry, and temperature), and ECG data will be displayed by time, with grades identified where appropriate. Additionally, a shift table of selected laboratory tests will be used to summarize the baseline and maximum post-baseline severity grade.

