5.10 ANALYSES FOR PERIOD B AND OPEN-LABEL EXTENSION STUDY

This section will pre-specify the main analyses planned for Study Period B of this study and the potential OLE study.

If the Sponsor decides to terminate the study based on the primary analysis results from Study Period A, all the data and analyses from Study Period B will be considered as exploratory in nature; a final CSR will be written, including these extra data. However, if the Sponsor decides to extend Study Period B or initiate an OLE study, a planned data snapshot will occur 2 years after finished the last efficacy visit in Study Period A.

Three analysis populations are defined for this snapshot:

- Study Period A mITT population: the mITT population defined in Section 4: all randomized participants who received at least 1 dose of study drug; participants are grouped according to the treatment assignment at randomization; all efficacy analyses in this snapshot are based on mITT population among the mutation carriers
- Study Period B safety population: all randomized participants that received at least 1 dose of study drug in Study Period B; participants are grouped according to the actual treatment received; participants on placebo who received more than 2 doses of crenezumab will be grouped in the crenezumab arm
- OLE safety population: all OLE enrolled participants that received at least 1 dose of study drug (crenezumab)

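### The two-dose clause in the SAP's safety-evaluable and tau-safety-evaluable definitions is not limited to placebo participants; read literally, it places a crenezumab participant who stops after dose 1 or 2 under placebo

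*SAP*

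**What the plan says.** The safety-evaluable row of SAP Section 4 admits every randomized participant with one or more doses of study drug. It then groups them in three steps:

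1. Participants are grouped by the treatment they actually received, crossed with mutation status.
2. Carriers and non-carriers who were randomized to placebo but had more than 2 crenezumab doses move to the crenezumab arm.
3. "all participants who have received no more than 2 doses of crenezumab will be further grouped together in a placebo arm", whatever their mutation status.

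Step 2 is expressly limited to participants randomized to placebo. Step 3 is not. The tau-safety-evaluable row has the same three steps in the same words.

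Two other definitions use the 2-dose threshold and limit it to placebo participants. The pharmacokinetic-evaluable row says that "participants randomized to placebo who received more than 2 doses of crenezumab will be grouped in the crenezumab arm". The Study Period B safety population in SAP Section 5.10 says that "participants on placebo who received more than 2 doses of crenezumab will be grouped in the crenezumab arm". Neither has a step 3.

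The definition carries weight. Section 5.1 states: "All safety analyses will be performed in the safety-evaluable population, unless otherwise specified". Section 5.6 says the same for Period A ("All safety analyses of Study Period A will be performed in the safety-evaluable population"), refers back to Section 4 and adds no restriction.

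Protocol Sections 3.6 and 4.10.4 group safety data by treatment received, with no dose threshold.

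**The concern.** A participant randomized to crenezumab who receives one or two crenezumab doses and stops is in the safety-evaluable set and meets step 3 as written. Step 1 puts that person under crenezumab and step 3 puts the same person under placebo.

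There is a documented route to such a case: protocol Sections 3.5.4.1 and 4.3.1.3 end dosing after a serious or severe hypersensitivity reaction. The early stoppers could therefore include people whose events matter to the safety profile. Applied literally, the rule could list such an event under placebo. The exposure summary (SAP 5.6.1) uses the same set, so a placebo column could also show crenezumab doses.

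The protocol cannot simply be relied on to correct this, because SAP Section 1 says: "The analyses specified in this document supersede the analysis plan described in the study protocol and the previous version of the SAP". Nor is the regrouping a declared change. SAP Appendix 1 lists departures from the protocol's planned analyses, and the only safety population named there is that of Period B. That list was drawn up against Protocol Version 10, whereas the protocol in hand is Version 11.

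**Working it through.** **Step 1: apply the wording.** No stated figure depends on this clause, so there is none to reproduce. The grouping steps were applied as written to three randomized groups (crenezumab carriers, placebo carriers, placebo non-carriers) with 0, 1, 2, 3 or 50 crenezumab doses, 15 combinations in all. The result was compared with a rule in which step 3 covers only placebo-randomized participants and those who received no crenezumab.

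| Randomized to | Crenezumab doses | As written | Limited rule |
|---|---|---|---|
| Crenezumab | 0 | placebo | placebo |
| Crenezumab | 1 | **placebo** | **crenezumab** |
| Crenezumab | 2 | **placebo** | **crenezumab** |
| Crenezumab | 3 or 50 | crenezumab | crenezumab |
| Placebo, carrier or non-carrier | 0, 1 or 2 | placebo | placebo |
| Placebo, carrier or non-carrier | 3 or 50 | crenezumab | crenezumab |

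The two rules differ in exactly two of the 15 combinations: crenezumab-randomized with 1 dose and with 2 doses.

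**Step 2: illustrate the size.** Inputs:

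- 84 + 84 carriers, from the simulation set-up in SAP Appendix 2 that mimics the study.
- 252 participants recruited, from protocol Section 3.2, giving 252 − 168 = 84 non-carriers.
- Assumed: these are the safety-set sizes, and no placebo participant has the event.
- k = crenezumab participants who stop after 1 or 2 doses and have the event (not given).
- m = other crenezumab participants with the event (not given).

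Grouped by treatment received, crenezumab against pooled placebo is (m + k)/84 v 0/168.

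*If the pooled arm replaces the base groups*, this becomes m/(84 − k) v k/(168 + k).

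- k = 0: no change.
- k = 1, m = 0: 1/84 (1.19%) v 0/168 becomes 0/83 (0%) v 1/169 (0.59%).
- k = 1, m = 3: 4/84 (4.76%) v 0/168 becomes 3/83 (3.61%) v 1/169 (0.59%). The difference falls from 4.76 to 3.02 points, in the same direction.
- The direction reverses only if m < k(84 − k)/(168 + k). The bound is 83/169 = 0.49 for k = 1, 164/170 = 0.96 for k = 2 and 243/171 = 1.42 for k = 3. Reversal therefore needs m = 0 for k = 1 or 2, and m = 0 or 1 for k = 3.

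*If the pooled arm is an added column*, the base groups remain.

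- k = 1, m = 0, carrier crenezumab v carrier placebo: 1/84 v 0/84, unchanged.
- k = 1, m = 0, crenezumab v pooled placebo: 1/84 (1.19%) v 1/169 (0.59%). The participant is counted in both columns, and the difference is 0.60 instead of 1.19 points.

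**The case against.** The strongest reply is that the intended meaning is plain. Step 3 follows a step about placebo-randomized participants and reads naturally as its complement. Its language of further grouping, regardless of mutation status, describes merging two existing placebo groups. The other two definitions fit this aim, since neither needs a pooling step. In Period B "all non-carriers will continue on placebo" while carriers receive crenezumab, and for pharmacokinetics "Samples from participants assigned to the placebo arms will not be analyzed except by request". This stands as the likely aim. It does not supply the missing limit, and no other current SAP text does so.

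The same language favours an added column over a replacement. The safety objective (protocol 2.2, SAP Table 1) and protocol Section 3.7 already make carrier crenezumab against carrier placebo the main comparison. Under the added-column reading that comparison is intact, and only the pooled one is diluted. This also stands.

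Early stopping for a reaction may be rare. Protocol Section 1.2.2.1 reports that in sporadic AD nearly all injection and infusion reactions were non-serious and did not alter study treatment. Under protocol Section 4.5.6, some who stopped treatment could return on IV dosing and so pass 2 doses, though not those who stopped for a drug-related event. Expedited reporting and the unblinded iDMC review do not depend on this definition. Disposition is tabulated on the ITT set and adverse events on the safety set by design, so a difference between those tables is not in itself a defect.

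A reader might infer that crenezumab events will be hidden under placebo, or that a safety signal would be reversed. The documents support neither. They give no count of participants with only 1 or 2 doses, and reversal needs the replacement reading together with almost no other crenezumab participant having the event.

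**Conclusion.** The concern holds as a wording defect of minor severity. In both rows, the literal rule misplaces crenezumab-randomized participants with 1 or 2 crenezumab doses and conflicts with grouping by treatment received in the same definition and in the protocol. That conclusion rests on the text alone.

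The consequence is conditional. The number affected is unknown and may be zero, in which case nothing changes. With one affected participant, the effect is confined to the pooled comparison under the added-column reading, and reaches the main safety tables only if the pooled arm replaces the base groups. All the percentages rest on 84 per group and no placebo events; they illustrate and do not predict.

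Primary and secondary efficacy use the mITT set grouped as randomized and are not affected. Nor does the clause leave the main safety comparison undefined, since the safety objective and protocol Section 3.7 already give it.

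**What to change.** In the safety-evaluable and tau-safety-evaluable rows of SAP Section 4:

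- Limit the last clause to participants randomized to placebo with no more than 2 crenezumab doses, plus any participant who received only placebo. The second part keeps in the placebo arm a crenezumab-randomized participant who, through a dosing error, never received crenezumab.
- State that crenezumab-randomized participants who received at least 1 dose of crenezumab stay in the crenezumab arm.

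The second statement is a small analysis choice: a crenezumab-randomized participant given mostly placebo in error would still count under crenezumab. It agrees with grouping by drug received and is best made explicit.

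The cost is one phrase and one sentence in each of two table rows. No new data are needed and no efficacy analysis changes.
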